8.9.3 Clinical Laboratory Evaluation

Urine pregnancy test results will be presented in a by-subject listing.

8.9.4 Other Observations Related to Safety

8.9.4.1 Cutaneous Safety Assessments

Descriptive statistics by visit will be provided for dryness and scaling.

Cutaneous Safety Assessments will be presented in a by-subject listing.

8.9.4.2 Local Tolerability Assessments

Descriptive statistics by visit will be provided for itching and burning/stinging.

Local tolerability data will be presented in a by-subject listing.

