18.4. Safety Evaluation

Safety will be evaluated by tabulations of adverse events (AEs), Cutaneous Safety Assessments for dryness and scaling, Local Tolerability Assessment for itching and burning and assessments for erythema and telangiectasia will be presented with descriptive statistics at Baseline and at the scheduled study visits. Frequencies and percentages for each outcome category will be included in these statistics. Safety data will be presented for patients in the Safety Population with tabulations for the following periods 12 to 28 weeks, > 28 to 52 weeks and > 52 weeks to the end of the study, as well as an overall for all periods.

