8.1.2 Baseline Definition

Baseline is defined as the last non-missing assessment prior to first application in 54-01/02. For all subjects enrolled in 54-01/54-02, the baseline values from 54-01/54-02 will be considered the baseline values for calculations in 54-07. Missing results will not be flagged as baseline.

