8.8.2.1 RosaQoL

The mean change in RosaQoL subscale scores from Baseline to Weeks 12, 24, 36, 48 and 52 will be summarized using descriptive statistics.

The subscores for the RosaQoL are computed as follows:

Total Score: the unweighted mean of all RosaQoL questions

Symptom subscale score: the unweighted mean of the following symptom questions

My rosacea burns or stings (item #2)

My rosacea is irritated (item #6)

My rosacea makes my skin sensitive (item #9)

My skin feels bumpy (uneven, not smooth, irregular) (item #16)

My skin flushes (item #17)

My skin gets irritated easily (cosmetics, aftershaves, cleansers) (item #18)

My eyes bother me (feels dry or gritty) (item #19)

Functional subscale score: the unweighted mean of the following functional questions

I try to cover up my rosacea (with make-up) (item #13)

I avoid certain foods or drinks because of my rosacea (item #15)

I avoid certain environments (heat, humidity, cold) because of my rosacea (item #21)

Emotion subscale score: the unweighted mean of the following emotion questions

- I worry that my rosacea may be serious (item #1)
- I worry about getting scars from my rosacea (item #3)
- I worry that my rosacea may get worse (item #4)
- I worry about side effects from rosacea medications (item #5)
- I am embarrassed by my rosacea (item #7)
- I am frustrated by my rosacea (item #8)
- I am annoyed by my rosacea (item #10)
- I am bothered by the appearance of my skin (redness, blotchiness) (item #11)
- My rosacea makes me feel self-conscious (item #12)
- I am bothered by persistence/reoccurrence of my rosacea (item #14)
- I think about my rosacea (item #20)

Each individual item should be scored as follows: 1=Never, 2=Rarely, 3=Sometimes, 4=Often, and 5=All the time. Missing data values will not be used. If a subscale has items with missing results, the subscore and the total will not be calculated.

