8.9.4.3 Vital Signs

Vital sign measurements include heart rate (HR), sitting blood pressure (BP) (both systolic and diastolic), body temperature, and weight. The data will be summarized with descriptive statistics by visit. In addition, the changes from Baseline will be summarized with descriptive statistics.

Vital sign data will be presented in a by-subject listing.

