1 – Mild	xx (xx.x%)		xx (xx.x%)
2 – Moderate	xx (xx.x%)		xx (xx.x%)
3 – Severe	xx (xx.x%)		xx (xx.x%)

^a Baseline is defined as the baseline value from SGT-54-01/SGT-54-02.

^b Table summaries based analysis visits, representing time from first dose of E-BPO 5% Cream.

SOURCE: USERNAME\SPONSOR\PROJECT\JOBNAME (DATE,TIME)

Table 14.3.1.1: Summary of Cutaneous Safety and Tolerability Evaluations
(Safety Population)
(Page 5 of 20)

	SGT-54-01/SGT-54-02 Vehicle Cream (N=xxx)	SGT-54-01/SG-54-02 E-BPO 5% Cream (N=xxx)	SGT-54-07 E-BPO 5% Cream (N=xxx)
Dryness			
Week 48 ^b			
n	xx	NA	xx
0 – None	xx (xx.x%)		xx (xx.x%)
1 – Mild	xx (xx.x%)		xx (xx.x%)
2 – Moderate	xx (xx.x%)		xx (xx.x%)
3 – Severe	xx (xx.x%)		xx (xx.x%)
Week 52 ^b			
n	xx	NA	xx
0 – None	xx (xx.x%)		xx (xx.x%)
1 – Mild	xx (xx.x%)		xx (xx.x%)
2 – Moderate	xx (xx.x%)		xx (xx.x%)
3 – Severe	xx (xx.x%)		xx (xx.x%)

^a Baseline is defined as the baseline value from SGT-54-01/SGT-54-02.

^b Table summaries based analysis visits, representing time from first dose of E-BPO 5% Cream.

SOURCE: USERNAME\SPONSOR\PROJECT\JOBNAME (DATE,TIME)

Repeat these pages for [Scaling, Itching and Burning/Stinging]

Table 14.3.1.2.1: Summary of Treatment-Emergent Adverse Event Characteristics
 (Safety Population)
 (Page 1 of 2)

	E-BPO 5% Cream (N=xxx)	
Subjects Reporting Any Treatment-Emergent Adverse Event	xx	(xx.x%)
Number of Treatment-Emergent Adverse Events	xx	
Subjects Reporting Any Serious Treatment-Emergent Adverse Event	xx	(xx.x%)
Number of Serious Treatment-Emergent Adverse Events	xx	
Subjects Reporting Treatment-Emergent Adverse Event with Outcome of Fatal	xx	(xx.x%)
Number of Treatment-Emergent Adverse Events with Outcome of Fatal	xx	
Subjects Who Discontinued Study Drug Due to a Treatment-Emergent Adverse Event	xx	(xx.x%)
Number of Treatment-Emergent Adverse Events Leading to Discontinuation of Study Drug	xx	
Subjects Who Discontinued from the Study Due to a Treatment-Emergent Adverse Event	xx	(xx.x%)
Number of Treatment-Emergent Adverse Events Leading to Discontinuation of Study	xx	

Note: Treatment-emergent adverse events are those events with an onset after the first application of E-BPO 5% Cream.
 Related defined as “Definitely”, “Probably”, or “Possible”. Not Related defined as “Unlikely” or “Not related”.

SOURCE: USERNAME\SPONSOR\PROJECT\JOBNAME (DATE, TIME)

Table 14.3.1.2.1: Summary of Treatment-Emergent Adverse Event Characteristics
 (Safety Population)
 (Page 2 of 2)

	E-BPO 5% Cream (N=xxx)	

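### The local safety scores are tabulated only as grade distributions per visit, so the tables cannot separate new or worsened reactions from persisting baseline symptoms

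*SAP*

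**What the plan says.** Dryness, scaling, itching and burning/stinging form one of the two safety endpoints in SAP Section 5 and Protocol Section 8. Protocol Sections 11 and 15 say that safety is assessed by monitoring the incidence of these assessments.

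The planned analysis is short. SAP 8.9.4.1 says "Descriptive statistics by visit will be provided for dryness and scaling", and SAP 8.9.4.2 says "Descriptive statistics by visit will be provided for itching and burning/stinging". The second continues "Local tolerability data will be presented in a by-subject listing", and 8.9.4.1 provides an equivalent listing. The shell of Table 14.3.1.1 gives n and the count and percentage at grades 0 to 3, at Baseline and at each analysis visit, for each sign. It has columns by prior treatment. It has no change, shift, worst-grade or worsened-since-Baseline block. Protocol 18.4 asks for no more: "Frequencies and percentages for each outcome category will be included in these statistics". For vital signs, by contrast, SAP 8.9.4.3 adds "In addition, the changes from Baseline will be summarized with descriptive statistics", and RosaQoL scores also get change from Baseline.

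On the reference value, SAP 8.1.2 says that "the baseline values from 54-01/54-02 will be considered the baseline values for calculations in 54-07". In the visit map of SAP 8.1.3, the first post-baseline row for prior-vehicle patients is SGT-54-07 Week 4.

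Protocol 15.1 and 15.2 keep these four reactions off the adverse event form unless they lead to a temporary stop of product, discontinuation from the study, or a new concomitant medication.

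**The concern.** Two processes can move the same score in opposite directions. Burning and irritation can be symptoms of rosacea: RosaQoL items 2 and 6 ask about exactly these (SAP 8.8.2.1). They can also be reactions to the product: SAP Section 4 lists dry skin, peeling and burning among the most frequent events with topical benzoyl peroxide. Baseline is taken before the first parent-trial application. The Protocol synopsis says that new patients must meet the parent trials' criteria, and Protocol 12.2 requires an IGA of 3 or 4, so Baseline reflects active disease.

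A per-visit distribution nets any improvement in disease symptoms against any new reaction. A reader who sees the percentage with burning fall could conclude that few patients developed burning, which the table cannot show. A new moderate reaction that the patient tolerates without stopping product or taking medication enters no adverse event table. It is counted in Table 14.3.1.1 together with symptoms that were there from the start.

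For prior-vehicle patients there is a second gap. Their Baseline row and their Week 4 row are separated by 12 weeks of vehicle as well as by their first S5G4T-1 exposure, so even the net movement is not a before-and-after comparison for the product.

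**Working it through.** There is no planned figure to reproduce. SAP Section 9 bases the sample size on a minimum requirement, and no document gives a distribution for these scores. The check is therefore how far the planned cells determine the number of patients with a new reaction. All prevalences below are assumptions.

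**1. New onset from two visit percentages.** Let p0 be the share with any grade (1 to 3) at Baseline, p1 the share at a later visit, and N the share at grade 0 at Baseline and grade 1 or more at the visit. The table gives p0 and p1. N is limited only by

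max(0, p1 − p0) ≤ N ≤ min(p1, 1 − p0).

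With p0 = 40% and p1 = 20%, the lower limit is max(0, −20%) = 0% and the upper limit is min(20%, 60%) = 20%. On the planned 700 patients that is 0 to 140.

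| Assumed p0 | Assumed p1 | N, lower | N, upper | Of 700 |
|---|---|---|---|---|
| 20% to 50% | 5% | 0% | 5% | 0 to 35 |
| 20% to 50% | 10% | 0% | 10% | 0 to 70 |
| 20% to 50% | 15% | 0% | 15% | 0 to 105 |
| 20% to 50% | 20% | 0% | 20% | 0 to 140 |

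The lower limit is 0% throughout, and the upper limit is the prevalence shown at the visit.

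**2. All four grades.** Take Baseline 60/25/12/3% and visit 80/14/5/1% at grades 0/1/2/3. Over all joint distributions with these margins, the share worsening by at least one grade runs from 0% to 20%. If the two scores were independent it would be 0.60 × 0.20 + 0.25 × 0.06 + 0.12 × 0.01 = 13.6%.

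**3. Moderate or severe only, two scenarios.**
- 25% at grade 2 or 3 at Baseline, 80% of them improve, and 8% of the rest newly reach grade 2 or 3. The visit shows 0.25 × 0.20 + 0.75 × 0.08 = 11%, of which 0.75 × 0.08 = 6 points are new.
- 5%, 80% and 2%. The visit shows 0.05 × 0.20 + 0.95 × 0.02 = 2.9%, of which 1.9 points are new.

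In both the displayed percentage falls (25% to 11%, 5% to 2.9%) and contains the new cases without identifying them.

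**4. Ever affected.** A flat 5% at each of 13 visits (Weeks 4 to 52, prior-S5G4T-1 patients) fits anything from 5% of patients ever affected (the same patients each time) to 13 × 5% = 65% (different patients each time). For the 10 visits of prior-vehicle patients the range is 5% to 50%.

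**5. Prior-vehicle reference.** SAP 8.1.2 takes their Baseline from before the parent trial. The SAP 8.1.3 map assigns their SGT-54-07 entry visit to no analysis visit. The last score before S5G4T-1 can start is therefore listed but not tabulated.

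**The case against.** The strongest reply is that the SAP delivers what the protocol defined: scores at Baseline and every visit, as category frequencies. The other ordinal scales (IGA, erythema, telangiectasia) are treated alike, in a descriptive study without testing. That stands. This is a gap in what the tables can answer, not a departure from Protocol 18.4.

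Several stronger readings are tempting, and the documents do not support them.

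- *The scores go unreported.* Listing 16.2.7.1 gives each patient's grade at each visit, including the prior-vehicle entry score. It has no change column, however, and runs to as many as 700 × 14 × 4 = 39,200 entries, so it does not replace a summary.
- *New reactions are invisible.* They are counted inside the displayed prevalence and cannot exceed it. What is lost is the split between new and persisting.
- *No other table would show them.* Reactions that meet one of the three conditions in Protocol 15.1 and 15.2 are adverse events and enter those tables.
- *All four scores start high and fall as rosacea improves.* No document reports a baseline score. Overlap with disease symptoms is documented for burning/stinging and irritation only; for dryness, scaling and itching it is an inference.
- *Any rise above the reference is a product reaction.* Product is not dispensed at IGA 0 or 1, so some scores come from patients off product, and a rise there may be a rosacea flare.

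The sponsor's 12-week phase 2 study (SAP Section 4) is also reassuring on severity. No patient had severe dryness, scaling or pruritus after baseline, and one on 5% had severe stinging and burning, recorded as an adverse event. That says little about moderate reactions or about use up to 52 weeks.

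**Conclusion.** The point holds in a limited form. For a named safety endpoint, the summary tables give prevalence by visit and cannot give the number of patients with new or worsened local reactions, although the protocol speaks of incidence. The size cannot be fixed from the documents. Under assumed any-grade prevalences of 20% to 50% at Baseline and 5% to 20% later, new onset at a visit is undetermined between 0% and the displayed 5% to 20%. Low displayed prevalence would cap the concern at that visit, though not across visits. The masking argument is firm for burning/stinging and inferred for the other signs. The missing entry score of prior-vehicle patients follows directly from SAP 8.1.2 and 8.1.3 and needs no assumption.

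This should be changed before database lock, which SAP Section 2 allows. It affects neither sample size nor conduct.

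**What to change.** For each sign, within the existing prior-treatment columns of Table 14.3.1.1, add:

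1. The reference grade as its own row: the last score before first S5G4T-1 application. For prior-S5G4T-1 patients this is the present Baseline. For prior-vehicle patients it is the SGT-54-07 entry score, or a later one if first dosed later.
2. The number and percentage of patients whose grade is above that reference, at each visit and for the worst grade after first dose.
3. The number and percentage newly at grade 2 or 3, at the same points.
4. A split of these counts by whether the patient was using product in the interval before the visit, taken from the dosing intervals already used in SAP 8.9.1.

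State the denominators, and amend SAP 8.9.4.1 and 8.9.4.2 to match. While the shell is open, correct its Weeks 44 to 52. It marks the prior-E-BPO column as not applicable, whereas the SAP 8.1.3 map says that those weeks are unavailable for prior-vehicle patients.

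The cost is programming only. Two counts × 4 signs × (13 visits + 1 worst grade) = 112 rows, or up to 224 with the product-use split, plus the reference rows and a second reference derivation for prior-vehicle patients. No new data are needed.

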8.9.4.3 Vital Signs

Vital sign measurements include heart rate (HR), sitting blood pressure (BP) (both systolic and diastolic), body temperature, and weight. The data will be summarized with descriptive statistics by visit. In addition, the changes from Baseline will be summarized with descriptive statistics.

Vital sign data will be presented in a by-subject listing.

8.9.4.4 Physical Examination

Physical examination data will be presented in a by-subject listing.

9. DETERMINATION OF SAMPLE SIZE

The sample size for this study was based on the minimum requirement for a long-term safety study.

10. CHANGES IN THE PLANNED ANALYSES

The protocol was written in a way that subjects who did not participate in 54-01 or 54-02 could be enrolled into 54-07. When the SAP was created, 54-07 was fully enrolled, and no subject was enrolled who did not complete the 54-01 or 54-02 study. The SAP was written such that any text from the protocol that discusses the new subjects was excluded.

Table 14.3.1.4.1: Summary of Treatment-Emergent Serious Adverse Event Characteristics (Safety Population).....	82
Table 14.3.1.4.2: Summary of Treatment-Emergent Serious Adverse Events by MedDRA System Organ Class and Preferred Term (Safety Population).....	84
Table 14.3.1.4.3: Summary of Serious Treatment-Emergent Adverse Events by Severity (Safety Population)	85
Table 14.3.1.4.4: Summary of Treatment-Emergent Serious Adverse Events by Relationship to Study Drug (Safety Population)	86
Table 14.3.1.5.1: Summary of Treatment-Emergent Serious Adverse Event Characteristics – By Period (Safety Population)	87
Table 14.3.1.5.2: Summary of Treatment-Emergent Serious Adverse Events by MedDRA System Organ Class and Preferred Term – By Period (Safety Population)	89
Table 14.3.1.5.3: Summary of Treatment-Emergent Serious Adverse Events by Severity – By Period (Safety Population)	90
Table 14.3.1.5.4: Summary of Treatment-Emergent Serious Adverse Events by Relationship to Study Drug – By Period (Safety Population).....	91
Table 14.3.1.4.1: Summary of Vital Signs (Safety Population)	92

**Table 14.0.1: Summary of Subject Completion/Discontinuation
(All Enrolled Subjects)**

	SGT-54-01/SGT-54-02 Vehicle Cream (N=xxx)	SGT-54-01/SG-54-02 E-BPO 5% Cream (N=xxx)	SGT-54-07 E-BPO 5% Cream (N=xxx)
Completed Study			
Yes	xx (xx.x%)	xx (xx.x%)	xx (xx.x%)
No	xx (xx.x%)	xx (xx.x%)	xx (xx.x%)
Reason for Discontinuation			
Adverse Event	xx (xx.x%)	xx (xx.x%)	xx (xx.x%)
Lost to Follow-Up	xx (xx.x%)	xx (xx.x%)	xx (xx.x%)
Lack of Efficacy	xx (xx.x%)	xx (xx.x%)	xx (xx.x%)
Pregnancy	xx (xx.x%)	xx (xx.x%)	xx (xx.x%)
Protocol Violation	xx (xx.x%)	xx (xx.x%)	xx (xx.x%)
Withdrawal by Subject	xx (xx.x%)	xx (xx.x%)	xx (xx.x%)
Study Terminated by Sponsor	xx (xx.x%)	xx (xx.x%)	xx (xx.x%)
Physician Decision	xx (xx.x%)	xx (xx.x%)	xx (xx.x%)
Worsening of Condition	xx (xx.x%)	xx (xx.x%)	xx (xx.x%)
Other	xx (xx.x%)	xx (xx.x%)	xx (xx.x%)

SOURCE: USERNAME\SPONSOR\PROJECT\JOBNAME (DATE, TIME)

**Table 14.0.2.1: Summary of Subject Enrollment and Evaluability
(All Enrolled Subjects)**

	SGT-54-01/SGT-54-02 Vehicle Cream (N=xxx)	SGT-54-01/SG-54-02 E-BPO 5% Cream (N=xxx)	SGT-54-07 E-BPO 5% Cream (N=xxx)
Number of Subjects Included in the Safety Population	xx (xx.x%)	xx (xx.x%)	xx (xx.x%)
Number of Subjects Excluded from the Safety Population	xx (xx.x%)	xx (xx.x%)	xx (xx.x%)
Reasons Excluded from the Safety Population ^a			
No Documented use of Study Drug	xx (xx.x%)	xx (xx.x%)	xx (xx.x%)
No Post Baseline Safety Assessment	xx (xx.x%)	xx (xx.x%)	xx (xx.x%)

^a Table includes primary reason (assigned in order presented in table) for reason subject was excluded.

SOURCE: USERNAME\SPONSOR\PROJECT\JOBNAME (DATE,TIME)

**Table 14.1.1.1: Summary of Subject Demographic Characteristics
(Safety Population)**

	SGT-54-01/SGT-54-02 Vehicle Cream (N=xxx)	SGT-54-01/SG-54-02 E-BPO 5% Cream (N=xxx)	SGT-54-07 E-BPO 5% Cream (N=xxx)
Age (years)			
n	xx	xx	xx
Mean	xx.x	xx.x	xx.x
SD	xx.xx	xx.xx	xx.xx
Median	xx.x	xx.x	xx.x
Min. to Max.	xx to xx	xx to xx	xx to xx
Sex			
n	xx	xx	xx
Male	xx (xx.x%)	xx (xx.x%)	xx (xx.x%)
Female	xx (xx.x%)	xx (xx.x%)	xx (xx.x%)
Ethnicity			
n	xx	xx	xx
Hispanic or Latino	xx (xx.x%)	xx (xx.x%)	xx (xx.x%)
Not Hispanic or Latino	xx (xx.x%)	xx (xx.x%)	xx (xx.x%)
Not Reported/Unknown	xx (xx.x%)	xx (xx.x%)	xx (xx.x%)
Race			
n	xx	xx	xx
American Indian or Alaska Native	xx (xx.x%)	xx (xx.x%)	xx (xx.x%)
Asian	xx (xx.x%)	xx (xx.x%)	xx (xx.x%)
Black or African American	xx (xx.x%)	xx (xx.x%)	xx (xx.x%)
Native Hawaiian or Other Pacific Islander	xx (xx.x%)	xx (xx.x%)	xx (xx.x%)
White	xx (xx.x%)	xx (xx.x%)	xx (xx.x%)
Multiple/Other ^a	xx (xx.x%)	xx (xx.x%)	xx (xx.x%)

^a See Listing 16.2.4.1 for a complete list of other races.

SOURCE: USERNAME\SPONSOR\PROJECT\JOBNAME (DATE,TIME)

Table 14.1.2.1: Subject Baseline Characteristics
(Safety Population)
(Page 1 of 2)

	SGT-54-01/SGT-54-02 Vehicle Cream (N=xxx)	SGT-54-01/SG-54-02 E-BPO 5% Cream (N=xxx)	SGT-54-07 E-BPO 5% Cream (N=xxx)
Height (cm)			
n	xx	xx	xx
Mean	xx.x	xx.x	xx.x
SD	xx.xx	xx.xx	xx.xx
Median	xx.x	xx.x	xx.x
Min. to Max.	xx to xx	xx to xx	xx to xx
Weight (kg)			
n	xx	xx	xx
Mean	xx.x	xx.x	xx.x
SD	xx.xx	xx.xx	xx.xx
Median	xx.x	xx.x	xx.x
Min. to Max.	xx to xx	xx to xx	xx to xx
BMI (kg/m²)			
n	xx	xx	xx
Mean	xx.x	xx.x	xx.x
SD	xx.xx	xx.xx	xx.xx
Median	xx.x	xx.x	xx.x
Min. to Max.	xx to xx	xx to xx	xx to xx

SOURCE: USERNAME\SPONSOR\PROJECT\JOBNAME (DATE,TIME)

Table 14.1.2.1: Subject Baseline Characteristics
(Safety Population)
(Page 2 of 2)

	SGT-54-01/SGT-54-02 Vehicle Cream (N=xxx)	SGT-54-01/SG-54-02 E-BPO 5% Cream (N=xxx)	SGT-54-07 E-BPO 5% Cream (N=xxx)
Inflammatory Lesion Count			
n	xx	xx	xx
Mean	xx.x	xx.x	xx.x
SD	xx.xx	xx.xx	xx.xx
Median	xx.x	xx.x	xx.x
Min. to Max.	xx to xx	xx to xx	xx to xx
Investigator Global Assessment			
n	xx	xx	xx
0 - Clear	xx (xx.x%)	xx (xx.x%)	xx (xx.x%)
1 - Almost Clear	xx (xx.x%)	xx (xx.x%)	xx (xx.x%)
2 - Mild	xx (xx.x%)	xx (xx.x%)	xx (xx.x%)
3 - Moderate	xx (xx.x%)	xx (xx.x%)	xx (xx.x%)
4 - Severe	xx (xx.x%)	xx (xx.x%)	xx (xx.x%)

SOURCE: USERNAME\SPONSOR\PROJECT\JOBNAME (DATE,TIME)

Table 14.1.3.1: Summary of Medical History by System Organ Class and Preferred Term
 (Safety Population)
 (Page 1 of xx)

System Organ Class Preferred Term	E-BPO 5% Cream (N=xxx)	
	By Subject ^a	By Event ^b
Number (%) of Subjects Reporting at Least One Medical History Term	xx (xx.x%)	
System Organ Class	xx (xx.x%)	xx
Preferred Term	xx (xx.x%)	xx

^a Counts reflect number of subjects reporting one or more medical history terms that map to MedDRA. At each level of summarization (System Organ Class or Preferred Term) subjects are counted once. Percentages are based on the number of subjects in the safety population.

^b Counts reflect number of medical history terms that map to MedDRA.

Note: MedDRA Version 21.0

SOURCE: USERNAME\SPONSOR\PROJECT\JOBNAME (DATE,TIME)

{NOTE TO PROGRAMMER: The table will be sorted by overall descending frequency of SOC and then, within a SOC, by overall descending frequency of Preferred Term}

Table 14.1.4.1: Summary of Concomitant Medications by ATC Level 2 and Preferred Name
 (Safety Population)
 (Page 1 of xx)

ATC Level 2 Term ^a Preferred Name	E-BPO 5% Cream (N=xxx)
Number (%) of Subjects Reporting at Least One Concomitant Medication	xx (xx.x%)
ATC Level 2 Term	xx (xx.x%)
Preferred Name	xx (xx.x%)

^a Counts reflect number of subjects reporting one or more medications that map to the WHO term. At each level of summarization (ATC Level 2 Term or Preferred Name) subjects are counted once. Percentages are based on the number of subjects in the safety population.

Note: WHO Drug Global Dictionary, Format B3, Version March 1, 2018

Concomitant medications are those used on/after the date of first application of E-BPO 5% Cream (from SGT-54-01/SGT-54-02 or SGT-54-07).

SOURCE: USERNAME\SPONSOR\PROJECT\JOBNAME (DATE,TIME)

Table 14.2.1.1: Summary of Investigator Global Assessment at Baseline and Week 40
(Safety Population)

Investigator Global Assessment	SGT-54-01/SGT-54-02 Vehicle Cream (N=xxx)	SGT-54-01/SG-54-02 E-BPO 5% Cream (N=xxx)	SGT-54-07 E-BPO 5% Cream (N=xxx)
Baseline^a			
n	xx	xx	xx
0 - Clear	xx (xx.x%)	xx (xx.x%)	xx (xx.x%)
1 - Almost Clear	xx (xx.x%)	xx (xx.x%)	xx (xx.x%)
2 - Mild	xx (xx.x%)	xx (xx.x%)	xx (xx.x%)
3 - Moderate	xx (xx.x%)	xx (xx.x%)	xx (xx.x%)
4 - Severe	xx (xx.x%)	xx (xx.x%)	xx (xx.x%)
Week 40/ET^b			
n	xx	xx	xx
0 - Clear	xx (xx.x%)	xx (xx.x%)	xx (xx.x%)
1 - Almost Clear	xx (xx.x%)	xx (xx.x%)	xx (xx.x%)
2 - Mild	xx (xx.x%)	xx (xx.x%)	xx (xx.x%)
3 - Moderate	xx (xx.x%)	xx (xx.x%)	xx (xx.x%)
4 - Severe	xx (xx.x%)	xx (xx.x%)	xx (xx.x%)
Achieving Clear or Almost Clear			
Success	xx (xx.x%)	xx (xx.x%)	xx (xx.x%)
Failure	xx (xx.x%)	xx (xx.x%)	xx (xx.x%)

^a Baseline is defined as the baseline value from SGT-54-01/SGT-54-02.

^b Table summaries based on nominal visit Week 40/ET from SGT-54-07.

SOURCE: USERNAME\SPONSOR\PROJECT\JOBNAME (DATE,TIME)

Table 14.2.1.2: Summary of Investigator Global Assessment at Each Evaluation
(Safety Population)
(Page 1 of 7)

Investigator Global Assessment	SGT-54-01/SGT-54-02	SGT-54-01/SG-54-02	SGT-54-07
	Vehicle Cream (N=xxx)	E-BPO 5% Cream (N=xxx)	E-BPO 5% Cream (N=xxx)
Baseline^a			
n	xx	xx	xx
0 - Clear	xx (xx.x%)	xx (xx.x%)	xx (xx.x%)
1 - Almost Clear	xx (xx.x%)	xx (xx.x%)	xx (xx.x%)
2 - Mild	xx (xx.x%)	xx (xx.x%)	xx (xx.x%)
3 - Moderate	xx (xx.x%)	xx (xx.x%)	xx (xx.x%)
4 - Severe	xx (xx.x%)	xx (xx.x%)	xx (xx.x%)
Week 4^b			
n	xx	xx	xx
0 - Clear	xx (xx.x%)	xx (xx.x%)	xx (xx.x%)
1 - Almost Clear	xx (xx.x%)	xx (xx.x%)	xx (xx.x%)
2 - Mild	xx (xx.x%)	xx (xx.x%)	xx (xx.x%)
3 - Moderate	xx (xx.x%)	xx (xx.x%)	xx (xx.x%)
4 - Severe	xx (xx.x%)	xx (xx.x%)	xx (xx.x%)
Achieving Clear or Almost Clear			
Success	xx (xx.x%)	xx (xx.x%)	xx (xx.x%)
Failure	xx (xx.x%)	xx (xx.x%)	xx (xx.x%)

^a Baseline is defined as the baseline value from SGT-54-01/SGT-54-02.

^b Table summaries based analysis visits, representing time from first dose of E-BPO 5% Cream.

SOURCE: USERNAME\SPONSOR\PROJECT\JOBNAME (DATE,TIME)

Table 14.2.1.2: Summary of Investigator Global Assessment at Each Evaluation
(Safety Population)
(Page 2 of 7)

Investigator Global Assessment	SGT-54-01/SGT-54-02	SGT-54-01/SG-54-02	SGT-54-07
	Vehicle Cream (N=xxx)	E-BPO 5% Cream (N=xxx)	E-BPO 5% Cream (N=xxx)
Week 8^b			
n	xx	xx	xx
0 - Clear	xx (xx.x%)	xx (xx.x%)	xx (xx.x%)
1 - Almost Clear	xx (xx.x%)	xx (xx.x%)	xx (xx.x%)
2 - Mild	xx (xx.x%)	xx (xx.x%)	xx (xx.x%)
3 - Moderate	xx (xx.x%)	xx (xx.x%)	xx (xx.x%)
4 - Severe	xx (xx.x%)	xx (xx.x%)	xx (xx.x%)
 Achieving Clear or Almost Clear			
Success	xx (xx.x%)	xx (xx.x%)	xx (xx.x%)
Failure	xx (xx.x%)	xx (xx.x%)	xx (xx.x%)
 Week 12^b			
n	xx	xx	xx
0 - Clear	xx (xx.x%)	xx (xx.x%)	xx (xx.x%)
1 - Almost Clear	xx (xx.x%)	xx (xx.x%)	xx (xx.x%)
2 - Mild	xx (xx.x%)	xx (xx.x%)	xx (xx.x%)
3 - Moderate	xx (xx.x%)	xx (xx.x%)	xx (xx.x%)
4 - Severe	xx (xx.x%)	xx (xx.x%)	xx (xx.x%)
 Achieving Clear or Almost Clear			
Success	xx (xx.x%)	xx (xx.x%)	xx (xx.x%)
Failure	xx (xx.x%)	xx (xx.x%)	xx (xx.x%)

^a Baseline is defined as the baseline value from SGT-54-01/SGT-54-02.

^b Table summaries based analysis visits, representing time from first dose of E-BPO 5% Cream.

SOURCE: USERNAME\SPONSOR\PROJECT\JOBNAME (DATE,TIME)

Table 14.2.1.2: Summary of Investigator Global Assessment at Each Evaluation
(Safety Population)
(Page 3 of 7)

Investigator Global Assessment	SGT-54-01/SGT-54-02 Vehicle Cream (N=xxx)	SGT-54-01/SG-54-02 E-BPO 5% Cream (N=xxx)	SGT-54-07 E-BPO 5% Cream (N=xxx)
Week 16^b			
n	xx	xx	xx
0 - Clear	xx (xx.x%)	xx (xx.x%)	xx (xx.x%)
1 - Almost Clear	xx (xx.x%)	xx (xx.x%)	xx (xx.x%)
2 - Mild	xx (xx.x%)	xx (xx.x%)	xx (xx.x%)
3 - Moderate	xx (xx.x%)	xx (xx.x%)	xx (xx.x%)
4 - Severe	xx (xx.x%)	xx (xx.x%)	xx (xx.x%)
 Achieving Clear or Almost Clear			
Success	xx (xx.x%)	xx (xx.x%)	xx (xx.x%)
Failure	xx (xx.x%)	xx (xx.x%)	xx (xx.x%)
 Week 20^b			
n	xx	xx	xx
0 - Clear	xx (xx.x%)	xx (xx.x%)	xx (xx.x%)
1 - Almost Clear	xx (xx.x%)	xx (xx.x%)	xx (xx.x%)
2 - Mild	xx (xx.x%)	xx (xx.x%)	xx (xx.x%)
3 - Moderate	xx (xx.x%)	xx (xx.x%)	xx (xx.x%)
4 - Severe	xx (xx.x%)	xx (xx.x%)	xx (xx.x%)
 Achieving Clear or Almost Clear			
Success	xx (xx.x%)	xx (xx.x%)	xx (xx.x%)
Failure	xx (xx.x%)	xx (xx.x%)	xx (xx.x%)

^a Baseline is defined as the baseline value from SGT-54-01/SGT-54-02.

^b Table summaries based analysis visits, representing time from first dose of E-BPO 5% Cream.

SOURCE: USERNAME\SPONSOR\PROJECT\JOBNAME (DATE,TIME)

Table 14.2.1.2: Summary of Investigator Global Assessment at Each Evaluation
(Safety Population)
(Page 4 of 7)

Investigator Global Assessment	SGT-54-01/SGT-54-02	SGT-54-01/SG-54-02	SGT-54-07
	Vehicle Cream (N=xxx)	E-BPO 5% Cream (N=xxx)	E-BPO 5% Cream (N=xxx)
Week 24^b			
n	xx	xx	xx
0 - Clear	xx (xx.x%)	xx (xx.x%)	xx (xx.x%)
1 - Almost Clear	xx (xx.x%)	xx (xx.x%)	xx (xx.x%)
2 - Mild	xx (xx.x%)	xx (xx.x%)	xx (xx.x%)
3 - Moderate	xx (xx.x%)	xx (xx.x%)	xx (xx.x%)
4 - Severe	xx (xx.x%)	xx (xx.x%)	xx (xx.x%)
 Achieving Clear or Almost Clear			
Success	xx (xx.x%)	xx (xx.x%)	xx (xx.x%)
Failure	xx (xx.x%)	xx (xx.x%)	xx (xx.x%)
 Week 28^b			
n	xx	xx	xx
0 - Clear	xx (xx.x%)	xx (xx.x%)	xx (xx.x%)
1 - Almost Clear	xx (xx.x%)	xx (xx.x%)	xx (xx.x%)
2 - Mild	xx (xx.x%)	xx (xx.x%)	xx (xx.x%)
3 - Moderate	xx (xx.x%)	xx (xx.x%)	xx (xx.x%)
4 - Severe	xx (xx.x%)	xx (xx.x%)	xx (xx.x%)
 Achieving Clear or Almost Clear			
Success	xx (xx.x%)	xx (xx.x%)	xx (xx.x%)
Failure	xx (xx.x%)	xx (xx.x%)	xx (xx.x%)

^a Baseline is defined as the baseline value from SGT-54-01/SGT-54-02.

^b Table summaries based analysis visits, representing time from first dose of E-BPO 5% Cream.

SOURCE: USERNAME\SPONSOR\PROJECT\JOBNAME (DATE,TIME)

Table 14.2.1.2: Summary of Investigator Global Assessment at Each Evaluation
(Safety Population)
(Page 5 of 7)

Investigator Global Assessment	SGT-54-01/SGT-54-02	SGT-54-01/SG-54-02	SGT-54-07
	Vehicle Cream (N=xxx)	E-BPO 5% Cream (N=xxx)	E-BPO 5% Cream (N=xxx)
Week 32^b			
n	xx	xx	xx
0 - Clear	xx (xx.x%)	xx (xx.x%)	xx (xx.x%)
1 - Almost Clear	xx (xx.x%)	xx (xx.x%)	xx (xx.x%)
2 - Mild	xx (xx.x%)	xx (xx.x%)	xx (xx.x%)
3 - Moderate	xx (xx.x%)	xx (xx.x%)	xx (xx.x%)
4 - Severe	xx (xx.x%)	xx (xx.x%)	xx (xx.x%)
 Achieving Clear or Almost Clear			
Success	xx (xx.x%)	xx (xx.x%)	xx (xx.x%)
Failure	xx (xx.x%)	xx (xx.x%)	xx (xx.x%)
 Week 36^b			
n	xx	xx	xx
0 - Clear	xx (xx.x%)	xx (xx.x%)	xx (xx.x%)
1 - Almost Clear	xx (xx.x%)	xx (xx.x%)	xx (xx.x%)
2 - Mild	xx (xx.x%)	xx (xx.x%)	xx (xx.x%)
3 - Moderate	xx (xx.x%)	xx (xx.x%)	xx (xx.x%)
4 - Severe	xx (xx.x%)	xx (xx.x%)	xx (xx.x%)
 Achieving Clear or Almost Clear			
Success	xx (xx.x%)	xx (xx.x%)	xx (xx.x%)
Failure	xx (xx.x%)	xx (xx.x%)	xx (xx.x%)

^a Baseline is defined as the baseline value from SGT-54-01/SGT-54-02.

^b Table summaries based analysis visits, representing time from first dose of E-BPO 5% Cream.

SOURCE: USERNAME\SPONSOR\PROJECT\JOBNAME (DATE,TIME)

Table 14.2.1.2: Summary of Investigator Global Assessment at Each Evaluation
(Safety Population)
(Page 6 of 7)

Investigator Global Assessment	SGT-54-01/SGT-54-02	SGT-54-01/SG-54-02	SGT-54-07
	Vehicle Cream (N=xxx)	E-BPO 5% Cream (N=xxx)	E-BPO 5% Cream (N=xxx)
Week 40^b			
n	xx	xx	xx
0 - Clear	xx (xx.x%)	xx (xx.x%)	xx (xx.x%)
1 - Almost Clear	xx (xx.x%)	xx (xx.x%)	xx (xx.x%)
2 - Mild	xx (xx.x%)	xx (xx.x%)	xx (xx.x%)
3 - Moderate	xx (xx.x%)	xx (xx.x%)	xx (xx.x%)
4 - Severe	xx (xx.x%)	xx (xx.x%)	xx (xx.x%)
 Achieving Clear or Almost Clear			
Success	xx (xx.x%)	xx (xx.x%)	xx (xx.x%)
Failure	xx (xx.x%)	xx (xx.x%)	xx (xx.x%)
 Week 44^b			
n	xx	NA	xx
0 - Clear	xx (xx.x%)		xx (xx.x%)
1 - Almost Clear	xx (xx.x%)		xx (xx.x%)
2 - Mild	xx (xx.x%)		xx (xx.x%)
3 - Moderate	xx (xx.x%)		xx (xx.x%)
4 - Severe	xx (xx.x%)		xx (xx.x%)
 Achieving Clear or Almost Clear			
Success	xx (xx.x%)		xx (xx.x%)
Failure	xx (xx.x%)		xx (xx.x%)

^a Baseline is defined as the baseline value from SGT-54-01/SGT-54-02.

^b Table summaries based analysis visits, representing time from first dose of E-BPO 5% Cream.

SOURCE: USERNAME\SPONSOR\PROJECT\JOBNAME (DATE,TIME)

Table 14.2.1.2: Summary of Investigator Global Assessment at Each Evaluation
(Safety Population)
(Page 7 of 7)

Investigator Global Assessment	SGT-54-01/SGT-54-02	SGT-54-01/SG-54-02	SGT-54-07
	Vehicle Cream (N=xxx)	E-BPO 5% Cream (N=xxx)	E-BPO 5% Cream (N=xxx)
Week 48^b			
n	xx	NA	xx
0 - Clear	xx (xx.x%)		xx (xx.x%)
1 - Almost Clear	xx (xx.x%)		xx (xx.x%)
2 - Mild	xx (xx.x%)		xx (xx.x%)
3 - Moderate	xx (xx.x%)		xx (xx.x%)
4 - Severe	xx (xx.x%)		xx (xx.x%)
Achieving Clear or Almost Clear			
Success	xx (xx.x%)		xx (xx.x%)
Failure	xx (xx.x%)		xx (xx.x%)
Week 52^b			
n	xx	NA	xx
0 - Clear	xx (xx.x%)		xx (xx.x%)
1 - Almost Clear	xx (xx.x%)		xx (xx.x%)
2 - Mild	xx (xx.x%)		xx (xx.x%)
3 - Moderate	xx (xx.x%)		xx (xx.x%)
4 - Severe	xx (xx.x%)		xx (xx.x%)
Achieving Clear or Almost Clear			
Success	xx (xx.x%)		xx (xx.x%)
Failure	xx (xx.x%)		xx (xx.x%)

^a Baseline is defined as the baseline value from SGT-54-01/SGT-54-02.

^b Table summaries based analysis visits, representing time from first dose of E-BPO 5% Cream.

SOURCE: USERNAME\SPONSOR\PROJECT\JOBNAME (DATE,TIME)

Table 14.2.2.1: Summary of RosaQoL Questionnaire Responses at Baseline and Week 40
(Safety Population)
(Page 1 of 4)

Total Score	SGT-54-01/SGT-54-02	SGT-54-01/SG-54-02	SGT-54-07
	Vehicle Cream	E-BPO 5% Cream	E-BPO 5% Cream
	(N=xxx)	(N=xxx)	(N=xxx)
Baseline^a			
n	xx	xx	xx
Mean	xx.x	xx.x	xx.x
SD	xx.xx	xx.xx	xx.xx
Median	xx.x	xx.x	xx.x
Min. to Max.	xx to xx	xx to xx	xx to xx
Week 40/ET^b			
n	xx	xx	xx
Mean	xx.x	xx.x	xx.x
SD	xx.xx	xx.xx	xx.xx
Median	xx.x	xx.x	xx.x
Min. to Max.	xx to xx	xx to xx	xx to xx
Absolute Change from Baseline			
n	xx	xx	xx
Mean	xx.x	xx.x	xx.x
SD	xx.xx	xx.xx	xx.xx
Median	xx.x	xx.x	xx.x
Min. to Max.	xx to xx	xx to xx	xx to xx

^a Baseline is defined as the baseline value from SGT-54-01/SGT-54-02.

^b Table summaries based on nominal visit Week 40/ET from SGT-54-07.

Note: Change calculated as Week 40/ET – Baseline. Negative values represent decrease from Baseline.

Total Score calculated from the unweighted mean of all RosaQoL questions.

Symptom Subscale Score calculated from items 2, 6, 9, 16, 17, 18, and 19.

Functional Subscale Score calculated from items 13, 15, and 21.

Emotional Subscale Score calculated from items 1, 3, 4, 5, 7, 8, 10, 11, 12, 14, and 20.

SOURCE: USERNAME\SPONSOR\PROJECT\JOBNAME (DATE,TIME)

Table 14.2.2.1: Summary of RosaQoL Questionnaire Responses at Baseline and Week 40
(Safety Population)
(Page 2 of 4)

Symptom Subscale Score	SGT-54-01/SGT-54-02	SGT-54-01/SG-54-02	SGT-54-07
	Vehicle Cream (N=xxx)	E-BPO 5% Cream (N=xxx)	E-BPO 5% Cream (N=xxx)
Baseline^a			
n	xx	xx	xx
Mean	xx.x	xx.x	xx.x
SD	xx.xx	xx.xx	xx.xx
Median	xx.x	xx.x	xx.x
Min. to Max.	xx to xx	xx to xx	xx to xx
Week 40/ET^b			
n	xx	xx	xx
Mean	xx.x	xx.x	xx.x
SD	xx.xx	xx.xx	xx.xx
Median	xx.x	xx.x	xx.x
Min. to Max.	xx to xx	xx to xx	xx to xx
Absolute Change from Baseline			
n	xx	xx	xx
Mean	xx.x	xx.x	xx.x
SD	xx.xx	xx.xx	xx.xx
Median	xx.x	xx.x	xx.x
Min. to Max.	xx to xx	xx to xx	xx to xx

^a Baseline is defined as the baseline value from SGT-54-01/SGT-54-02.

^b Table summaries based on nominal visit Week 40/ET from SGT-54-07.

Note: Change calculated as Week 40/ET – Baseline. Negative values represent decrease from Baseline.

Total Score calculated from the unweighted mean of all RosaQoL questions.

Symptom Subscale Score calculated from items 2, 6, 9, 16, 17, 18, and 19.

Functional Subscale Score calculated from items 13, 15, and 21.

Emotional Subscale Score calculated from items 1, 3, 4, 5, 7, 8, 10, 11, 12, 14, and 20.

SOURCE: USERNAME\SPONSOR\PROJECT\JOBNAME (DATE,TIME)

Table 14.2.2.1: Summary of RosaQoL Questionnaire Responses at Baseline and Week 40
(Safety Population)
(Page 3 of 4)

Functional Subscale Score	SGT-54-01/SGT-54-02	SGT-54-01/SG-54-02	SGT-54-07
	Vehicle Cream (N=xxx)	E-BPO 5% Cream (N=xxx)	E-BPO 5% Cream (N=xxx)
Baseline^a			
n	xx	xx	xx
Mean	xx.x	xx.x	xx.x
SD	xx.xx	xx.xx	xx.xx
Median	xx.x	xx.x	xx.x
Min. to Max.	xx to xx	xx to xx	xx to xx
Week 40/ET^b			
n	xx	xx	xx
Mean	xx.x	xx.x	xx.x
SD	xx.xx	xx.xx	xx.xx
Median	xx.x	xx.x	xx.x
Min. to Max.	xx to xx	xx to xx	xx to xx
Absolute Change from Baseline			
n	xx	xx	xx
Mean	xx.x	xx.x	xx.x
SD	xx.xx	xx.xx	xx.xx
Median	xx.x	xx.x	xx.x
Min. to Max.	xx to xx	xx to xx	xx to xx

^a Baseline is defined as the baseline value from SGT-54-01/SGT-54-02.

^b Table summaries based on nominal visit Week 40/ET from SGT-54-07.

Note: Change calculated as Week 40/ET – Baseline. Negative values represent decrease from Baseline.

Total Score calculated from the unweighted mean of all RosaQoL questions.

Symptom Subscale Score calculated from items 2, 6, 9, 16, 17, 18, and 19.

Functional Subscale Score calculated from items 13, 15, and 21.

Emotional Subscale Score calculated from items 1, 3, 4, 5, 7, 8, 10, 11, 12, 14, and 20.

SOURCE: USERNAME\SPONSOR\PROJECT\JOBNAME (DATE,TIME)

Table 14.2.2.1: Summary of RosaQoL Questionnaire Responses at Baseline and Week 40
(Safety Population)
(Page 4 of 4)

Emotional Subscale Score	SGT-54-01/SGT-54-02	SGT-54-01/SG-54-02	SGT-54-07
	Vehicle Cream	E-BPO 5% Cream	E-BPO 5% Cream
	(N=xxx)	(N=xxx)	(N=xxx)
Baseline^a			
n	xx	xx	xx
Mean	xx.x	xx.x	xx.x
SD	xx.xx	xx.xx	xx.xx
Median	xx.x	xx.x	xx.x
Min. to Max.	xx to xx	xx to xx	xx to xx
Week 40/ET^b			
n	xx	xx	xx
Mean	xx.x	xx.x	xx.x
SD	xx.xx	xx.xx	xx.xx
Median	xx.x	xx.x	xx.x
Min. to Max.	xx to xx	xx to xx	xx to xx
Absolute Change from Baseline			
n	xx	xx	xx
Mean	xx.x	xx.x	xx.x
SD	xx.xx	xx.xx	xx.xx
Median	xx.x	xx.x	xx.x
Min. to Max.	xx to xx	xx to xx	xx to xx

^a Baseline is defined as the baseline value from SGT-54-01/SGT-54-02.

^b Table summaries based on nominal visit Week 40/ET from SGT-54-07.

Note: Change calculated as Week 40/ET – Baseline. Negative values represent decrease from Baseline.

Total Score calculated from the unweighted mean of all RosaQoL questions.

Symptom Subscale Score calculated from items 2, 6, 9, 16, 17, 18, and 19.

Functional Subscale Score calculated from items 13, 15, and 21.

Emotional Subscale Score calculated from items 1, 3, 4, 5, 7, 8, 10, 11, 12, 14, and 20.

SOURCE: USERNAME\SPONSOR\PROJECT\JOBNAME (DATE,TIME)

Table 14.2.2.2: Summary of RosaQoL Questionnaire Responses at Each Evaluation
(Safety Population)
(Page 1 of 24)

Total Score	SGT-54-01/SGT-54-02	SGT-54-01/SG-54-02	SGT-54-07
	Vehicle Cream	E-BPO 5% Cream	E-BPO 5% Cream
	(N=xxx)	(N=xxx)	(N=xxx)
Baseline^a			
n	xx	xx	xx
Mean	xx.x	xx.x	xx.x
SD	xx.xx	xx.xx	xx.xx
Median	xx.x	xx.x	xx.x
Min. to Max.	xx to xx	xx to xx	xx to xx
Week 12^b			
n	xx	xx	xx
Mean	xx.x	xx.x	xx.x
SD	xx.xx	xx.xx	xx.xx
Median	xx.x	xx.x	xx.x
Min. to Max.	xx to xx	xx to xx	xx to xx
Absolute Change from Baseline			
n	xx	xx	xx
Mean	xx.x	xx.x	xx.x
SD	xx.xx	xx.xx	xx.xx
Median	xx.x	xx.x	xx.x
Min. to Max.	xx to xx	xx to xx	xx to xx

^a Baseline is defined as the baseline value from SGT-54-01/SGT-54-02.

^b Table summaries based analysis visits, representing time from first dose of E-BPO 5% Cream.

Note: Change calculated as post-Baseline – Baseline. Negative values represent decrease from Baseline.

Total Score calculated from the unweighted mean of all RosaQoL questions.

Symptom Subscale Score calculated from items 2, 6, 9, 16, 17, 18, and 19.

